Clinical Assessment of Skin Quality and Efficacy of Dermal Line Improvement Following Four Bipolar Radiofrequency Microneedling Treatments

NCT 05085730

Document Date: 11/17/2022

Clinical Assessment of Skin Quality and Efficacy of Dermal Line Improvement Following Four Bipolar Radiofrequency Microneedling Treatments

[REDACTED]	[REDACTED]
[REDACTED]	[REDACTED]
PRINCIPAL INVESTIGATOR	[name], MD
SUB-INVESTIGATORS	[name], MD [name], MBe

[REDACTED]

[REDACTED]

[REDACTED]

[REDACTED]

[REDACTED]

[REDACTED]

[REDACTED]

[REDACTED]

2. Purpose

The primary objective of this study is to evaluate the safety and efficacy of a bipolar fractional radiofrequency treatment via use of the InMode Morpheus8 System to achieve skin texture and quality change and to treat facial fine lines and wrinkles of the lower face.

[figure not shown]
3. Study Design

This is a single center, unblinded, non-randomized, non-controlled study designed to follow a total of up to thirteen (13) qualified and consenting subjects receiving 4 bipolar fractional radiofrequency microneedling treatment of the lower face, once every 4-6 weeks for a total of 4 treatments, under an IRB approved protocol. Following these treatments, patients will have follow-up visits at 3-months, and 6-months post-treatment. The effects of bipolar fractional radiofrequency treatments via the InMode Morpheus8 System will be determined by subjective and objective analysis through clinician and subject assessments.

Overall assessment of clinical outcome and safety will be based on clinic visits and evaluation of pre- and post-procedural photos. These photos will be identifiable full face photos, and subjects will be adequately informed of such. One unblinded clinician's assessments of satisfaction will be characterized using the Lemperle Wrinkle Assessment Scale, a four-point Allergan skin fine line scale and a four-point Allergan Skin Roughness scale at baseline, 3 month follow up and 6 month follow up visits. The five-point Global Aesthetic Improvement Scale (GAIS) will also be used at 3 month and 6 month follow up visits. Additionally, evaluation of pre- and post-procedural photos will be performed comparing baseline and follow ups by blinded raters. In conjunction with standard and close-up photography, subjects will also have photos taken using the VISIA Imaging system and will undergo high-resolution ultrasonography, transepidermal water loss (TEWL) measurements and/or BTC 2000 measurements for exploratory purposes. High-resolution ultrasound will be utilized for assessment of skin thickness and density. TEWL measurements are taken via the Bio Aquaflux and will be used to evaluate barrier function of the skin epidermal layer to determine progress of epidermal healing after treatment and BTC

2000 will be used to measure skin laxity, viscoelastic deformation, stiffness, energy absorption, elasticity and deformation values of skin. Additionally consenting subjects will undergo skin biopsies at the treatment site to better qualify the measurements and results from the items mentioned above. Micro-biopsies using 0.33mm size punches will be used to extract core tissues pre- and post-treatment for histological evaluation (tissue structure, elastin, collagen and hyaluronic acid expression) and gene expression assessment (elastin, other major ECM molecules and elastin related genes).

From these exploratory procedures the improvement in skin quality and dermal lines of the lower face and jawline can be evaluated in comparison to pre-treatment assessments.

5. Eligibility Criteria

5.1. Inclusion Criteria

- 1 Healthy male and female adults between ages 21-70 years of age.
- 2 Presence of facial dermal lines and skin changes of the lower face associated with age or environmental exposure.
- 3 Subjects who can read, understand, and sign the Informed Consent Form.
- 4 Subjects willing and able to comply with all study requirements.
- 5 Fitzpatrick skin type I-VI.
- 6 Minimum of 1 on the Lemperle Wrinkle Assessment Scale, Allergan Fine Line Scale and Allergan Skin Roughness Scale
- 7 Subject is willing not to undergo any type of aesthetic procedure that could confound the study device treatment effects until he/she completes the study.

5.2. Exclusion Criteria:

- 1 Active localized or systemic infections, that may alter wound healing.
- 2 Immunocompromised subjects.
- 3 Subjects with coagulation disorder.
- 4 History of skin photosensitivity disorders, or use of photosensitizing drugs (e.g., tetracycline or sulfa drugs).
- 5 Pregnant and/or lactating (All female volunteers will be advised about using birth control during the period of study).
- 6 5 on the Lemperle Wrinkle Assessment Scale or 4 on the Allergan Fine Line Scale and/or Allergan Skin Roughness Scales
- 7 Scarring in areas to be treated.
- 8 Tattoos in the treatment areas to be treated.
- 9 Significant open facial wounds or lesions.
- 10 Severe or cystic acne in treatment areas.
- 11 Current active smoker.
- 12 Use of Accutane (Isotretinoin) within the past 6 months.
- 13 Use of topical retinoids within 48 hours.
- 14 Use of prescription anticoagulants.
- 15 Pacemaker or internal defibrillator.
- 16 History of skin disorders resulting in abnormal wound healing (i.e. keloids, extreme dry and fragile skin).
- 17 Subjects on current oral corticosteroid therapy or within the past 6 months
- 18 Metal implants in the treatment area.
- 19 In the opinion of the investigator, subject is unwilling or unable to adhere to all study requirements, including application and follow-up visits.
- 20 Subjects with a history of radiation therapy to the treatment area.
- 21 Subject has a history of allergy to lidocaine or ester-based local anesthetics.
- 22 Subjects with significant cardiac history or rhythm disturbance who may be unable to tolerate lidocaine with epinephrine.

- 23 Subjects with any skin pathology or condition in the treatment area that could interfere with evaluation or with the use of typical ancillary medical treatments or care used before, during or after treatments (e.g. psoriasis, rosacea, eczema, seborrheic dermatitis, vitiligo, hyper or hypo-skin pigmentation conditions such as post inflammatory hyperpigmentation).
- 24 Subjects who are unwilling to shave excessive hair in the treatment area that might influence or impair evaluation in the opinion of the Investigator.
- 25 Subjects have undergone skin resurfacing or tightening treatments in the treatment area over the past year.
- 26 Subjects have undergone dermatological treatments such as fillers and neurotoxins for the past 6 months in the treatment area.
- 27 Subjects have undergone laser and light treatments in the treatment area over the past 3 months.
- 28 Subjects who have undergone surgery in the proposed treatment area within the past 3 months.
- 29 Subjects have undergone superficial peel or microdermabrasion within 4 weeks.

6. Study Endpoints

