11.1. Assessment of Facial Wrinkling

Assessment of facial wrinkling will be performed at baseline and at 3-months and 6-months post-treatment. Facial wrinkling will be assessed using the Lemperle Wrinkle Assessment Scale⁹. Wrinkling in the following regions- forehead, glabellar folds, periorbital, preauricular areas, cheek, nasolabial folds, upper lip, marionette lines, corners of mouth, chin, and neck- can be assessed according to scale's definitions (See Appendix I).

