11.2. Assessment of Fine Lines

Assessment of fine lines will be performed at baseline and at 3-months and 6-months post-treatment. Fine lines will be assessed using the Allergan Fine Line Scales for Facial Fine Lines¹¹. Fine lines on the midface/cheeks will be assessed according to the scale's definitions (See Appendix IIa and IIb).

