11.7. Imaging Procedures

Prior to photography procedures, clinic personnel will ensure that subjects have a clean face and neck with no makeup as described in the study procedures. Subjects will remove any jewelry from the area(s) to be photographed and equilibrate for at least 15 minutes to ambient conditions within the clinic before any photographs are taken. Subjects will be provided with a headband or hair tie to keep hair away from the face.

Subjects will be instructed to adopt neutral, non-smiling expressions with their eyes gently closed for VISIA. Subjects will be carefully positioned for each photograph, directly facing the camera for the center view and turned at a 45° angle for the right and left side views.

1 *VISIA Complexion Analysis*

Digital images will be taken of each applicable subject with fine lines and wrinkles on the face using the VISIA Complexion Analysis System at baseline, 3-months post-treatment, and 6-months post-treatment. Each subject will have a total of 3 full-face images taken (right side, left side, and center view) using the following lighting conditions:

Standard lighting 1: visible (bright)

Standard lighting 2: visible (flat)

Cross-polarized:

UV-NF

2 *NIKON D7100*

Standard, close-up and cross-polarized photography of the face and neck will be utilized for evaluation of fine lines and wrinkles. These photographs will be taken utilizing the Nikon D7100 at baseline, 3-months post-treatment, and 6-months post-treatment.

11.8. *Noninvasive Procedures*

Biox Aquaflux will be used to measure transepidermal water loss (TEWL) measurements which evaluate barrier function of the skin epidermal layer to determine progress of epidermal healing after treatment. The BTC 2000 will be used to measure skin laxity, viscoelastic deformation, stiffness, energy absorption, elasticity, and deformation values of skin. All procedures will be performed on the submental area.

11.9. *Skin Biopsies*

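### The washouts for earlier cosmetic procedures (Exclusions 25-28) cover only the treatment area, but primary outcomes are also scored on skin outside it, so an earlier effect that is still changing there is attributed to the device

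*Combined protocol and SAP*

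**What the plan says.** Section 3 describes a "single center, unblinded, non-randomized, non-controlled study" of up to 13 subjects who receive four treatments of the lower face, 4 to 6 weeks apart.

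Section 5.2 has four washouts for earlier procedures, each limited to the treatment area:

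- Exclusion 25, one year: "Subjects have undergone skin resurfacing or tightening treatments in the treatment area over the past year".
- Exclusion 26, six months: "fillers and neurotoxins for the past 6 months in the treatment area".
- Exclusion 27, three months: "Subjects have undergone laser and light treatments in the treatment area over the past 3 months".
- Exclusion 28, three months: surgery in the proposed treatment area.

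Two neighbouring rules have no area limit. Exclusion 29 bars a recent peel or microdermabrasion anywhere. Inclusion 7 asks subjects to forgo "any type of aesthetic procedure that could confound the study device treatment effects" until they complete the study.

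The outcomes cover a wider field. Section 11.2 states "Fine lines on the midface/cheeks will be assessed". Section 11.3 grades roughness on the midface. Section 11.4 bases the CGAIS on photographs of the face and neck. Section 11.1 lists Lemperle regions that can be assessed, beginning "forehead, glabellar folds, periorbital, preauricular areas, cheek" and ending with the neck. For TEWL and BTC 2000, Section 11.8 says "All procedures will be performed on the submental area". Section 12 analyses change from baseline and tests the mean CGAIS against 4 (no change).

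**The concern.** A washout lets the effect of an earlier procedure settle before baseline, so that later change can be credited to the study treatment. That works only if it covers the skin on which the outcome is read. Here the washed-out area and the scored area are defined separately and do not match. A subject with recent midface laser or resurfacing outside the treated zone meets no exclusion in the visible text, yet the midface carries two of the primary scales.

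Nothing later in the plan separates such drift from a device effect. There is no concurrent group. Each subject is compared with his or her own baseline. The three blinded photograph readers in Section 11.10 do not help, because they would correctly grade a real change in the skin. Inclusion 7 looks forward only. By barring repeat procedures that could confound, it also means that a recent filler or neurotoxin wears off during follow-up without being renewed.

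**Working it through.** The plan gives no figure on this point, so there is none to reproduce. The check sets the area wording side by side and then adds scale.

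**1. Scored area against washed-out area**

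| Outcome | Area scored | Covered by Exclusions 25-28? |
|---|---|---|
| Fine lines (primary, 11.2) | Midface/cheeks | At most in part; some cheek may count as treated |
| Roughness (primary, 11.3) | Midface | At most in part |
| CGAIS (primary, 11.4) | Face and neck photographs | Lower-face part only |
| Lemperle (primary, 11.1) | Up to 11 regions, forehead to neck | Not forehead, glabella or periorbital; neck unclear |
| TEWL, BTC 2000 (11.8; secondary in 6.2, within the primary outcome measure in Section 12) | Submental | Cannot be settled from the visible text |

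**2. Time over which an earlier effect can change**

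Objective assessments at baseline fall at Visit 2 (Treatment 1) in the Schedule of Events. Reading post-treatment as after Treatment 4:

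- Treatment 1 to Treatment 4: 3 × 4 = 12 to 3 × 6 = 18 weeks.
- Month 3: 12 + 13 = 25 to 18 + 13 = 31 weeks after baseline.
- Month 6: 12 + 26 = 38 to 18 + 26 = 44 weeks after baseline.

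The change score therefore spans roughly 6 to 10 months.

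**3. Shift in the mean change**

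Assume that k of 13 subjects drift by one grade for reasons unrelated to the device. On a single-region scale the shift is k/13. On an 11-region Lemperle average it is (k/13) × (regions affected/11). The four regions used are forehead, glabella, periorbital and neck; seven adds preauricular, cheek and nasolabial.

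| k | Single-region scale | Lemperle, 4 of 11 | Lemperle, 7 of 11 |
|---|---|---|---|
| 1 | 0.08 | 0.03 | 0.05 |
| 2 | 0.15 | 0.06 | 0.10 |
| 4 | 0.31 | 0.11 | 0.20 |

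**4. Does this produce false positives for the device?**

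Only under some assumptions. The simulation used n = 13, no device effect, grading noise of -1/0/+1 with probabilities 0.2/0.6/0.2, a one-grade drift in a given share of subjects, and a two-sided paired t-test at 0.05. The shares, the noise, the drift, the test and the alpha are all assumptions. Section 12 names a paired comparison but no test or alpha for these scales. The chance of a significant result in favour of the device was:

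| Direction of drift | 0% share | 10% | 20% | 30% |
|---|---|---|---|---|
| All improving | about 2.5% | 5.7% | 11.8% | 21.6% |
| Half improving, half waning | about 2.5% | 2.2-2.5% | 2.2% | 2.3% |
| All waning | about 2.5% | 0.9% | 0.2-0.3% | 0.1% |

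The result depends on the direction of drift, which the documents do not give. By symmetry, all-waning drift gives false worsening at the rates in the first row, and it would mask a real benefit.

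**The case against.** The strongest reply is that the gap may be smaller than it looks and that its effect has no fixed direction. Several stronger readings that a reader might infer are not supported.

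- **That any earlier procedure counts as device effect.** It does not. Baseline is measured after the procedure, so a stable effect cancels in the change score. Only an effect that moves between baseline and follow-up matters.
- **That the plan tilts the result towards the device.** The 5.7% to 21.6% rates hold only if all drift is improvement. Mixed drift gives no inflation, and waning drift works against the device. Nor does the six-month window in Exclusion 26 state how long a neurotoxin or filler effect lasts, so the timing of any waning cannot be read from it.
- **That submental or cheek procedures are certainly allowed.** The exact boundary of the treatment area is not in the visible text, and parts of the protocol are blacked out. Section 3 says lower face. The text after it also speaks of the jawline and places biopsies at the treatment site, which Section 11.9 locates on the cheek beside the upper lip. Some cheek, and possibly submental skin, may already be covered.
- **That upper-face grades certainly enter the endpoint.** Section 11.1 says only that the regions can be assessed, and Section 6.1 calls the scale modified.
- **That Exclusion 23 is part of the same problem.** It concerns skin disease, so nothing about earlier procedures follows from it.

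All of this narrows the point without removing it. The midface scales are stated as assessments that will be done, the CGAIS takes in the face and neck, and no plausible reading of lower face includes the forehead or periorbital skin.

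**Conclusion.** The mismatch is in the text and should be corrected. It is firmest for the fine-line and roughness scales and for the CGAIS. It is conditional for the upper-face and neck Lemperle regions, and open for the submental measurements. In an uncontrolled change-from-baseline analysis, an earlier procedure whose effect is still building or fading in scored but unwashed skin is attributed to the device.

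The size and direction of the bias are unknown, because the documents give neither a rate nor a type of earlier procedure. The one-grade drift behind the 0.08 grade per affected subject is an assumption. The simulated error rates illustrate sensitivity to direction and are not an estimate for this trial. This is a cheap improvement to the eligibility wording; it does not show that the result will be biased in the device's favour.

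**What to change.** In Exclusions 25, 26, 27 and 28, replace the limit to the treatment area (proposed treatment area in 28) with a limit to any area that is treated, graded or measured. Keep each time window as written.

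Alongside this, state the treatment area explicitly and reconcile it with the regions scored in Sections 11.1 to 11.4 and measured in 11.8, including which Lemperle regions enter the endpoint. Recording the date and site of earlier procedures in the medical history would let any remaining drift be examined.

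Keep Exclusion 23 out of this change. Its wording about interference with evaluation can be reconciled with the scored regions separately.

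The cost is a wording change in four criteria and somewhat slower recruitment, because candidates with recent procedures elsewhere on the face or neck must wait or are excluded. How much slower cannot be judged from the documents. Restricting the endpoints to treated skin would also remove most of the mismatch, but it would change how the primary outcomes are assessed.

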6.1. Primary Endpoints

- 1 Improvement of fine lines and wrinkle severity using a modified Lemperle Wrinkle Assessment Scale, the Allergan Scale for Fine Lines and the Allergan Skin Roughness Scale Assessment at baseline, 3-months, and 6-months post-treatment
- 2 Clinician's Global Aesthetic Improvement Scale (CGAIS) at 3-months and 6-months post-treatment

* TEWL measurement, BTC-2000, and/or high frequency ultrasound images will be taken

11. Assessments

Note that the order of the assessments listed below may be altered from the order indicated in the study visits in order to help study flow, or at the recommendations of the Sponsor or Investigator. Any change in the order of procedures will not compromise study data.

11.1. Assessment of Facial Wrinkling

Assessment of facial wrinkling will be performed at baseline and at 3-months and 6-months post-treatment. Facial wrinkling will be assessed using the Lemperle Wrinkle Assessment Scale⁹. Wrinkling in the following regions- forehead, glabellar folds, periorbital, preauricular areas, cheek, nasolabial folds, upper lip, marionette lines, corners of mouth, chin, and neck- can be assessed according to scale's definitions (See Appendix I).

11.2. Assessment of Fine Lines

Assessment of fine lines will be performed at baseline and at 3-months and 6-months post-treatment. Fine lines will be assessed using the Allergan Fine Line Scales for Facial Fine Lines¹¹. Fine lines on the midface/cheeks will be assessed according to the scale's definitions (See Appendix IIa and IIb).

11.3. Allergan Skin Roughness Scale

Assessment of skin roughness will be performed at baseline and at 3-months and 6-months post-treatment. Skin roughness will be assessed using the Allergan Skin Roughness Scale¹³. Skin roughness will be assessed according to the scale's definitions based on descriptions of severity of skin coarseness, crosshatching and elastosis in the midface area (See Appendix IIIa and IIIb).

11.4. Clinician's Global Aesthetic Improvement Scale (CGAIS)

Subjective assessment of aesthetic improvement will be performed at 3-months and 6-months post-treatment (See Appendix IV).

The scale should be completed in two steps:

- 1 Based on a live assessment of the subject while referring to the subject's pre-treatment photographs of the face and neck, and
- 2 Based on a comparison of the subject's pre-treatment photographs to the current post-treatment photographs of the face and neck.

11.5. Subject's Global Aesthetic Improvement Scale (SGAIS)

Subjective assessment of aesthetic improvement will be performed at 3-months and 6-months post-treatment (See Appendix IV).

11.6. Patient Satisfaction Questionnaire

Subjective assessment of patient satisfaction will be performed at 3-months and 6-months post-treatment (See Appendix V).

11.7. Imaging Procedures

Prior to photography procedures, clinic personnel will ensure that subjects have a clean face and neck with no makeup as described in the study procedures. Subjects will remove any jewelry from the area(s) to be photographed and equilibrate for at least 15 minutes to ambient conditions within the clinic before any photographs are taken. Subjects will be provided with a headband or hair tie to keep hair away from the face.

Subjects will be instructed to adopt neutral, non-smiling expressions with their eyes gently closed for VISIA. Subjects will be carefully positioned for each photograph, directly facing the camera for the center view and turned at a 45° angle for the right and left side views.

1 *VISIA Complexion Analysis*

Digital images will be taken of each applicable subject with fine lines and wrinkles on the face using the VISIA Complexion Analysis System at baseline, 3-months post-treatment, and 6-months post-treatment. Each subject will have a total of 3 full-face images taken (right side, left side, and center view) using the following lighting conditions:

Standard lighting 1: visible (bright)

Standard lighting 2: visible (flat)

Cross-polarized:

UV-NF

2 *NIKON D7100*

Standard, close-up and cross-polarized photography of the face and neck will be utilized for evaluation of fine lines and wrinkles. These photographs will be taken utilizing the Nikon D7100 at baseline, 3-months post-treatment, and 6-months post-treatment.

11.8. *Noninvasive Procedures*

Biox Aquaflux will be used to measure transepidermal water loss (TEWL) measurements which evaluate barrier function of the skin epidermal layer to determine progress of epidermal healing after treatment. The BTC 2000 will be used to measure skin laxity, viscoelastic deformation, stiffness, energy absorption, elasticity, and deformation values of skin. All procedures will be performed on the submental area.

11.9. *Skin Biopsies*

Two 0.33 mm punch biopsies will be taken from the cheek adjacent to the lateral upper lip at Visit 2, Visit 6 and Visit 7. Prior to biopsy the area will be cleaned with alcohol and a local numbing agent, 0.5%-1% Lidocaine with epinephrine, will be used to anesthetize the area being biopsied. If bleeding is present, pressure will be held on the biopsy site until bleeding stops. Immediately after collection, biopsies for histology and gene expression will be put in 4% PFA and RNA-Later solution, respectively. Biopsies will be stored in a cooler for transfer to the Plastic Surgery Research Lab at UTSW for molecular analysis.

11.10. *Blinded Evaluation*

Blinded evaluation will be performed by three qualified, non-treating clinicians to determine if the InMode Morpheus8 System is effective in improving the appearance of facial and neck skin quality and dermal lines.

At study conclusion, the Principal Investigator will select three blinded, physician evaluators to assess photos of subjects taken pre- and post-treatment. The evaluators will be trained

by the PI or research team member on the grading scales in order to independently review photographs for each subject. The evaluators will be blinded to subject information and will only know that the study consisted of multiple treatment visits and follow up visits at 3 months and 6 months. They will be provided a set of photos taken at three different visits – pre-treatment, 3 month post-treatment and 6 month post-treatment – in a randomized and unidentifiable order. No information will be provided that may allow them to determine the baseline from follow up imaging. Evaluators will be asked to assess the sets of pictures using the Lemperle Wrinkle, Allergan Fine Lines and Allergan Skin Roughness scales. After completion of the scales, the raters will be unblinded and asked to complete the Clinical Global Aesthetics Improved Scale (CGAIS).

The source documents will be prepared and distributed to the blinded evaluators by a member of the study staff. A decreased score for each assessment will indicate an improvement for the indicated parameters.

12. Statistical Methods of Analysis

This initial study will include change from baseline analysis.

The primary outcome measure of effectiveness will be a paired comparison of baseline to all applicable post-baseline time points using data obtained from transepidermal water loss assessments, high resolution ultrasonography, BTC 2000 measurements, biopsy results, and 3D imaging results. Photographs and 3D video of treated skin at follow-up visits will be compared to baseline for blinded scoring evaluations. Mean of the change from baseline (defined as post-baseline value minus baseline value) will be estimated at post-baseline time points for applicable parameters.

The following will be calculated and reported for each evaluation parameter at the applicable post-baseline time point(s):

$$\text{Percent mean change from baseline} = \frac{\text{(visit mean score} - \text{baseline mean score})}{\text{baseline mean score}} \times 100$$

For Clinician's Global Aesthetic Improvement Assessment, the null hypothesis that the mean score is equal to 4 (no change) will be tested.

13. Non-Significant Risk Determination

In accordance with the definition of "Significant Risk Device" provided in the U.S. Code of Federal Regulations 21 CFR 812.3, the study device to be used in this research study has been determined to be a Non-Significant Risk (NSR) device based on the following:

- a) It is not an implant

- b) It is not purported or represented to be for use in supporting or sustaining human life and do not present a potential for serious risk to the health, safety or welfare of a subject
- c) It is not for a use of substantial importance in diagnosing, curing, mitigating, or treating disease or otherwise preventing impairment of human health
- d) Use of the device poses no risk to the health, safety, or welfare of a subject

14. Device Description

The InMode Morpheus8 System is a minimally invasive bipolar radiofrequency (RF) microneedling device FDA-cleared for full-body adipose tissue remodeling. The fractional RF device, with adjustable penetration depth and energy delivery, contains 12-24 coated needles. During treatment, these needles penetrate and deliver thermal energy into the subdermal tissue, leading to coagulation of fat and contraction of the reticular dermis and surrounding connective tissue. Additionally, it is theorized that the thermal injury caused by the RF energy initiates the wound healing process, stimulating neocollagenesis, elastogenesis, and angiogenesis.

[figure not shown]
Image 1. InMode Morpheus8 System

Image 2. Morpheus8 Radiofrequency Microneedling Device

Image 3. Illustration of RF Microneedling Depth and Effect

15. Potential Risks

Blistering, burning, and infection: (Rare)

A crust, blister or superficial wound can occur at the treatment area. The risk of infection will be minimized by proper wound care.

Bruising: (Rare)

A mild bruising may occur at the treatment area as a result of radiofrequency exposure. This is usually transient and resolves in a few hours to few days.

Transient edema and/or erythema: (Occasionally)

May develop within the irradiated areas but are usually temporary and fade within 24-72 hours.

Pigmentary changes: (Rare)

Radiofrequency exposure can cause pigmentary changes such as hyper- (and hypopigmentation. Although this is usually temporary, it may be permanent on rare occasions. Sun avoidance and/or the use of a total sun block (SPF 30 or higher) will help minimize the intensity and duration of any pigmentary changes.

Scarring: (Rare)

As with any form of energy exposure, there is a small risk of scarring. However, this is minimized by proper technique and wound care.

Allergic Reaction: (Rare)

There is a possibility of an allergic or toxic reaction to anesthesia used to numb the areas. Subjects will be questioned with regard to any history of allergies and carefully monitored for signs of allergic reaction.

Biopsy

Risks associated with biopsy include: 1) scarring - a small risk of scarring, which can be mitigated by proper technique and wound care; 2) allergic reaction - there is a possibility of an allergic or toxic reaction to anesthesia used to numb the areas. Subjects will be questioned with regard to any history of allergies and carefully monitored for signs of allergic reaction.

Photography

The subject may be uncomfortable with sitting still for an extended period of time or from turning his/her body in various positions. Subjects may be sensitive to the bright and repeating flashes from the camera, which can sometimes cause headaches, irritation of the eyes, discomfort, aftereffects such as seeing spots, and in rare cases, could stimulate a migraine headache or epileptic seizure.

Photographs include a risk of identification, as these will be full face photos. Privacy will be protected to the greatest extent possible. Photos will only be identified by a unique subject identification number that contains no personal identifying information. All photos will be stored on a password secure drive, with only access by research personnel. For research purposes, photos may be used in scientific publications.

Noninvasive procedures (exploratory)

1. Biox Aquaflux will be used to measure transepidermal water loss (TEWL) measurements which evaluate barrier function of the skin epidermal layer to determine progress of epidermal healing after treatment. The standard time for TEWL measurements should take approximately 5 minutes.

2. The BTC 2000 will be used to measure skin laxity, viscoelastic deformation, stiffness, energy absorption, elasticity, and deformation values of skin. The standard time for BTC 2000 should take approximately 5 minutes.
3. The DUB Skin Scanner, a high-resolution ultrasound, will be used to assess skin thickness, epidermal thickness, and skin density. The standard time for DUB should take approximately 5 minutes.

All these tests are considered noninvasive, and no risks are anticipated.

16. Potential Benefits

Subjects may benefit by having an overall improvement in quality and texture of the skin as well as the presence of dermal lines of the lower face. There may be a benefit to the medical community by demonstrating the safety and effectiveness of a new technology in the management of skin quality of the lower face and jawline as well in the treatment of dermal lines. This technology may have advantages over existing technologies currently in use (lasers, ultrasound, etc.) because of its combination of bipolar fractional radiofrequency and microneedling technology. This technology may lead to better clinical outcomes for an understudied area.

17. Adverse Events

